5 SAFETY

The Principal Investigator is responsible for ensuring that all staff involved in the study is familiar with the content of this section.

5.1 Definition of adverse events

An adverse event (AE) is the development of an undesirable medical condition or the deterioration of a pre-existing medical condition following or during exposure to a pharmaceutical product, whether or not considered causally related to the product. An undesirable medical condition can be a symptom (eg, nausea, chest pain), sign (eg, tachycardia, enlarged liver) or the abnormal results of an investigation (eg, laboratory findings, electrocardiogram). In clinical studies, an AE can include an undesirable medical condition occurring at any time even if no study treatment has been administered.

The term AE is used to include both serious and non-serious AEs. The Common Terminology Criteria for Adverse Events (CTCAE) version 4.03 will be used to report AEs for this study.

5.2 Definitions of serious adverse event

A serious adverse event is an AE occurring during any study phase that fulfils one or more of the following criteria:

- Results in death not related to breast cancer disease progression
- Is immediately life-threatening
- Requires in-patient hospitalization or prolongation of existing hospitalization
- Results in persistent or significant disability or incapacity

- Is a congenital abnormality or birth defect
- Is an important medical event that may jeopardize the subject or may require medical intervention to prevent one of the outcomes listed above.

The causality of SAEs (their relationship to all study treatment/procedures) will be assessed by the Investigator(s) and documented or reported on the SAE eCRF page.

5.3 Definition of adverse events of special interest (AESI)

An adverse event of special interest (AESI) is one of scientific and medical interest specific to understanding of the Investigational Product and may require close monitoring and rapid communication by the investigator to the sponsor. An AESI may be serious or non-serious. The rapid reporting of AESIs allows ongoing surveillance of these events in order to characterize and understand them in association with the use of this investigational product.

AESIs for durvalumab include but are not limited to events with a potential inflammatory or immune-mediated mechanism and which may require more frequent monitoring and/or interventions such as steroids, immunosuppressants and/or hormone replacement therapy. These AESIs are being closely monitored in clinical studies with durvalumab monotherapy and combination therapy. An immune-related adverse event (irAE) is defined as an adverse event that is associated with drug exposure and is consistent with an immune-mediated mechanism of action and where there is no clear alternate aetiology. Serologic, immunologic, and histologic (biopsy) data, as appropriate, should be used to support an irAE diagnosis. Appropriate efforts should be made to rule out neoplastic, infectious, metabolic, toxin, or other etiologic causes of the irAE.

Only AESIs meeting serious criteria will be reported during the Extension period.

If the Investigator has any questions in regards to an adverse event (AE) being an irAE, the Investigator should promptly contact the Study Chair.

Criteria for Hy's Law (FDA Guidance 2009)

- The drug causes hepatocellular injury, generally shown by a higher incidence of 3-fold or greater elevations above the ULN of ALT or AST than the (non-hepatotoxic) control drug or placebo
- Among trial subjects showing such aminotransferase elevations, often with aminotransferases much greater than 3 x ULN, one or more also show elevation of serum total bilirubin to >2 x ULN, without initial findings of cholestasis (elevated serum alkaline phosphatase).
- No other reason can be found to explain the combination of increased aminotransferases and total bilirubin, such as viral hepatitis A, B, or C; pre-existing or acute liver disease; or another drug capable of causing the observed injury.

5.4 Recording of adverse events

For the Extension period, only SAEs will be reported in eCRFs. Non-serious AEs will be

managed according to the site's clinical practice and the toxicity management guidelines set forth in this protocol, but will not be reported in eCRFs.

Information about all SAEs, whether volunteered by the subject, discovered by Investigator questioning, or detected through physical examination, laboratory test, or other means, will be collected and recorded and followed as appropriate.

All SAEs, whether or not deemed drug-related, must be reported within IBM-CD (eCOS) by the site Investigator or qualified designee within 1 business day of first becoming aware of the event.

Questions about SAE reporting can be referred to DCRI Safety Surveillance at **[name], or at [name] within North America.**

If the IBM-CD system is temporarily unavailable, the event, including the Investigator-determined causality to study drug, should be reported via a paper back-up SAE form to DCRI Safety Surveillance. Upon return of the availability of IBM-CD system, the SAE information must be entered into IBM-CD.

The following variables will be collected in the eCRF during the Extension period for each SAE:

- SAE (verbatim per CTCAE)
- The date when the SAE started and stopped
- Changes in NCI CTCAE grade and the maximum CTC grade attained
- Investigator causality rating against the Investigational Product (yes or no) /combination drug (yes/no)
- Action taken with regard to investigational product /combination agent
- Outcome
- Date AE met criteria for serious AE
- Reason AE is defined as serious (fatal or life threatening, results in persistent or significant disability/incapacity, constitutes a congenital anomaly/birth defect, is medically significant, requires inpatient hospitalization or prolongation of existing hospitalization).
- Date of hospitalization
- Date of discharge
- Probable cause of death
- Date of death

- Autopsy performed
- Description of AE
- Causality assessment in relation to Study procedure(s)
- Causality assessment in relation to other medication
- Causality assessment in relation to additional study drug

It is important to distinguish between serious and severe AEs. Severity is a measure of intensity, whereas seriousness is defined by the criteria in Section 5.2. An AE of severe intensity need not necessarily be considered serious. For example, nausea that persists for several hours may be considered severe nausea, but not a SAE. On the other hand, a stroke that results in only a limited degree of disability may be considered a mild stroke but would be a SAE.

5.4.1 Time period for collection of adverse events and serious adverse events

All SAEs will be collected during the extension period through 30 days after the last dose of either drug or until the initiation of an alternative anticancer therapy. Please refer to the Schedule of Assessments in Appendix A.

5.5 Follow-up of unresolved serious adverse events

All SAEs should be treated appropriately. Such treatment may include changes in study drug treatment, including possible interruption or discontinuation, starting or stopping concomitant treatments, changes in the frequency or nature of assessments, hospitalization, or any other medically required intervention. Once an SAE is detected, it should be followed until its resolution, and assessment should be made at each visit (or more frequently, if necessary) of any changes in severity, the suspected relationship to the study drug, the interventions required to treat it, and the outcome.

5.6 Adverse events based on signs and symptoms

When collecting SAEs, the recording of diagnoses is preferred (when possible) to recording a list of signs and symptoms. However, if a diagnosis is known and there are other signs or symptoms that are not generally part of the diagnosis, the diagnosis and each sign or symptom will be recorded separately.

5.7 Adverse events based on examinations and tests

Deterioration as compared to baseline in protocol-mandated laboratory values, for vital signs should only be reported if they fulfil any of the SAE criteria or are the reason for discontinuation of treatment with the investigational product.

If deterioration in a laboratory value/vital sign is associated with clinical signs and symptoms, the sign or symptom will be reported as the event and the associated laboratory result/vital sign will be considered as additional information. Wherever possible the reporting Investigator uses the clinical, rather than the laboratory term (eg, anemia versus low hemoglobin value).

Deterioration of a laboratory value, which is unequivocally due to disease progression, should not be reported as an SAE

Cases where a subject shows an AST or ALT ≥ 3 xULN and total bilirubin ≥ 2 xULN may need to be reported as SAEs, please refer to Section 5.3 (AESI definition) for further instructions.

5.8 Disease progression

Disease progression can be considered as a worsening of a subject's condition attributable to the disease for which the investigational product is being studied. It may be an increase in the severity of the disease under study and/or increases in the symptoms of the disease. SAEs due to progression will be reported and classified as unrelated to treatment.

5.9 New cancers

The development of a new primary cancer should be regarded as an SAE since this event will generally meet at least one of the serious criteria (see Section 5.2). New primary cancers are those that are not the primary reason for the administration of the study treatment and have developed after the inclusion of the subject into the study. These do not include metastases of the original cancer. Symptoms of metastasis or the metastasis itself should not be reported as an AE/SAE, as they are considered to be disease progression.

5.10 Lack of efficacy

When there is deterioration in the condition for which the study treatment(s) is being used, mTNBC, there may be uncertainty as to whether this is lack of efficacy or an AE. In such cases, unless the Sponsor or the reporting physician considers that the study treatment contributed to the deterioration of the condition, or local regulations state to the contrary, the deterioration should be considered to be a lack of efficacy and not an AE.

5.11 Deaths

All deaths that occur during the study, or within the protocol-defined 30-day post-study follow-up period after the administration of the last dose of study treatment, must be reported as follows:

- Death that is clearly the result of disease progression should be documented in the eCRF but should not be reported as an SAE.
- Where death is not due (or not clearly due) to progression of the disease under study, the main or primary event causing the death must be documented in the eCRF as a SAE within **1 business day** (see Section 5.2 for further details). The report should contain a comment regarding the co-involvement of progression of disease, if appropriate, and should assign main and contributory causes of death.
- Deaths with an unknown cause should always be reported as a SAE. A post mortem maybe helpful in the assessment of the cause of death, and if performed a copy of the post-mortem results should be included within the eCRF.

5.12 Other events requiring reporting

5.12.1 Pregnancy

If a patient becomes pregnant during the course of the study, the IPs should be discontinued immediately.

Pregnancy itself is not regarded as an AE unless there is a suspicion that the IP under study may have interfered with the effectiveness of a contraceptive medication. Congenital abnormalities or birth defects and spontaneous miscarriages should be reported and handled as SAEs. Elective abortions without complications should not be handled as AEs. The outcome of all pregnancies (spontaneous miscarriage, elective termination, ectopic pregnancy, normal birth, or congenital abnormality) should be followed up and documented even if the patient was discontinued from the study.

If any pregnancy occurs in the course of the study, then the Investigator or other site personnel should inform the sponsor or their designated representatives within 1 business day, ie, immediately, but **no later than 1 business day** of when he or she becomes aware of it.

The same timelines apply when outcome information is available.

5.12.2 Reporting of serious adverse events

SAEs are reported with the eCRF database within 1 business day of the investigator's knowledge of the event.

* The investigative site must also indicate, the *causality* of events *in relation to all study medications* and if the SAE is *related to disease progression*, as determined by the site Principal Investigator.

5.12.3 Translational study

Biopsies and tissue specimen

At time of enrollment, all archival or fresh tissue obtained will be banked. This will be a requirement for participation in the study. Where possible, formalin-fixed paraffin embedded (FFPE) blocks are preferred. If blocks are unavailable, thirty unstained and unbaked 5-µm slides from each subject (minimum of 10 slides for pre-treatment biopsy/archival tissue required) should be processed as close to batch shipment date as possible. Post-treatment biopsy is encouraged but optional. All tissue will be banked at the site until the batch shipment date near full enrolment of the trial. Each sample will be labelled with Subject ID code and the required number of slides retained / shipped to the relevant research laboratories. All blood, tissue samples and buccal swabs will be processed centrally by the Duke BioRepository & Precision Pathology Center (BRPC). Shipping back to the Duke BioRepository & Precision Pathology Center (BRPC) will be arranged and communicated to the sites nearing the end of enrollment. Please see lab manual for further details.

All study subjects will have a buccal swab for germline DNA collected during screening; these will be banked at study sites until the end of the study.

Immunohistochemical HRD assay

Banked tumor samples will be profiled based on protein expression using multiplexed microscopy. The multiplexing ability of the Opal-Vectra system will be used to study different antibody combinations relevant to homologous recombination for all samples obtained in this

Whole exome sequencing (WES)

DNA samples will be obtained from the tumor samples and from the buccal DNA swabs that will be obtained during screening. PCR-based exon sequencing will be performed using standard techniques. Genetic variants will be characterized as missense, nonsense, and frameshift, and then will be narrowed by retaining only somatic rare variants and homozygous mutations. Wald testing will initially be used to define relationships between gene alterations and response to therapy.

We also have a very large set of profiled primary and metastatic TNBC samples (both carboplatin sensitive and insensitive) that will serve as a comparator set for the samples in this proposal (Blackwell, SABCS, 2013). We will be able to use this established and well-characterized set for quality control and gene mutation comparison.

Immune profiling

Immune profiling will be done using standard immunohistochemistry techniques. The following immune markers will be stained and quantitated using an experienced breast pathologist who will quantitate staining in tumor and in the stroma. The following markers will be assessed initially:

1. Quantitative TILs using H and E stained slide²¹

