2.3 Exploratory objectives

- To characterize the molecular epidemiology of biomarkers in TNBC through whole exome sequencing and immunohistochemistry studies.
- To explore the immune microenvironment of TNBC including, but not limited to, tumor-infiltrating lymphocytes (TILs), macrophages and others.

[figure not shown]
- To explore the tumor immunosuppressive microenvironment including but not limited to programmed death-ligand- 1 status on tumor and associated tissues.
- To analyze epigenetic changes in TNBC including, but not limited to, DNA methylation and non-coding RNAs such as miRNAs.
- To validate the role of minimally invasive blood-based markers such as circulating tumor cells or plasma DNA
- To perform mutational analysis on normal germline DNA obtained from blood samples and buccal swabs.
- Through systematic acquisition of tumor biopsies, additional tissue will be banked in the Duke Pathology central biorepository for future genetic research; it represents an invaluable resource toward achieving a deeper understanding of the mechanism of resistance or response to olaparib and or durvalumab.
- To compare patients randomized to olaparib and olaparib in combination with the durvalumab arm on their efficacy outcome measures.
- To determine the efficacy as assessed by PFS, ORR, duration of response of maintenance olaparib in combination with durvalumab based on iRECIST criteria

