3 STUDY DESIGN

3.1 Overall study structure and flow chart

This is a randomized, international, multicenter, Phase II study designed to explore the efficacy of olaparib or olaparib in combination with durvalumab in platinum-treated mTNBC (See Figure 1). The primary objectives are to explore olaparib or olaparib in combination with durvalumab as maintenance therapy following clinical benefit with platinum-based therapy in subjects with mTNBC.

Figure 1: Study Schema

Approximately 60 subjects with mTNBC who are receiving platinum-based chemotherapy and who have had no more than 2 lines of chemotherapy in the metastatic or advanced setting, with one of those being a platinum, will be enrolled. Subjects will be eligible for this study following a minimum of three 3-weekly cycles or six 1-weekly doses of platinum-based (cisplatin or carboplatin) chemotherapy as single agent or combination therapy as prescribed by their treating physician. Subjects can continue with further cycles of chemotherapy or be randomized any time after eligibility to allow for screening procedures to proceed without interruption of ongoing treatment. Subjects deriving clinical benefit (CR / PR / SD) with platinum-based therapy as determined by the treating physician will be eligible and randomized in a 1:1 ratio stratified by site and by the line of chemotherapy (in the metastatic setting). Randomization will be used to allocate subjects to either the olaparib or olaparib in combination with durvalumab arm, and comparisons between treatment regimens are planned as an exploratory objective. The purpose of randomization was to reduce bias due to subject selection into either treatment arm.

Germline BRCA mutation testing is not mandated for entry onto the trial; however, previous BRCA test data will be collected to ascertain the number of known BRCA mutation carriers -- which will be limited to 10 in total.

Tumor status will be evaluated as per RECIST v1.1 criteria. Tumor measurement for disease evaluation will be performed every 8 weeks on both arms, regardless of initial response to platinum chemotherapy. Estimation of PFS, duration of response and tumor response will be based on RECIST v1.1.

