7 STATISTICAL METHODS AND SAMPLE SIZE DETERMINATION

7.1 Statistical analyses and determination of sample size

Based upon current standard of care,³⁰ the median PFS (mPFS) in this population is estimated to be approximately 2 months, and a clinically relevant improvement with either of the proposed maintenance treatments would be to an mPFS of 4 months. In both arms of the study, it is proposed to test a null hypothesis of an mPFS of 2 months against an alternative hypothesis of an mPFS of 4 months. To test this hypothesis, assuming an exponential PFS distribution, use of an exponential MLE test, a two-sided significance level of 5% and a power of 90%, 25 subjects are required per arm. To allow for a drop-out rate of approximately 20%, the sample size per arm will be inflated to 30 subjects, for a total of 60 subjects.

Comparison between the two treatment arms will be performed as an exploratory analysis.

The number of subjects that will agree to participate in the genetic research is unknown. It is therefore not possible to establish whether sufficient data will be collected to allow a formal statistical evaluation or whether only descriptive statistics will be generated. A statistical analysis plan will be prepared where appropriate.

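### As written, the exome filter drops heterozygous germline variants, BRCA1/2 included, although germline mutational analysis is a stated objective with no other method

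*Combined protocol and SAP*

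**What the plan says.** Four parts of the protocol bear on this.

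- **Objective (section 2.3).** One exploratory aim reads "To perform mutational analysis on normal germline DNA obtained from blood samples and buccal swabs".
- **Samples (section 5.12.3).** "All study subjects will have a buccal swab for germline DNA collected during screening". For the exome work, "DNA samples will be obtained from the tumor samples and from the buccal DNA swabs that will be obtained during screening".
- **Filter and test (section 5.12.3, whole exome sequencing).** Variants are typed as missense, nonsense or frameshift, and "then will be narrowed by retaining only somatic rare variants and homozygous mutations". The sentence after that is "Wald testing will initially be used to define relationships between gene alterations and response to therapy". No exception is made for BRCA1/2, for other repair genes or for pathogenic germline variants.
- **BRCA status at entry (section 3.1).** "Germline BRCA mutation testing is not mandated for entry onto the trial". Instead, "previous BRCA test data will be collected to ascertain the number of known BRCA mutation carriers", and the number of known carriers is capped at 10.

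On analysis of the genetic data, section 7.1 says that participation is unknown and that "It is therefore not possible to establish whether sufficient data will be collected to allow a formal statistical evaluation". It foresees a further statistical analysis plan, but only conditionally.

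**The concern.** A person who carries a germline BRCA mutation ordinarily has one altered copy. In normal tissue that variant is germline and heterozygous, which is the class the filter leaves out. The buccal swab is collected from everyone expressly as a germline sample, but the one paragraph that says what happens to its sequence data excludes the usual carrier state.

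What is at stake is the exploratory link between gene alterations and response. Impaired DNA repair, including BRCA deficiency, is part of the rationale for olaparib (sections 1, 1.1.1 and 1.3). Because testing is not required at entry, the banked DNA is the only described route to germline status in subjects who were never tested. If their variants are filtered out, untested carriers sit in the unaltered group. If carriers do respond better, that would pull the altered-versus-unaltered contrast toward no difference.

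**Working it through.** No figure in the plan corresponds to this point, so there is nothing to reproduce. The check is to apply the written rule to each kind of variant and compare the result with the objective.

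**Step 1: the rule.** The sentence in section 5.12.3 can be parsed in two ways.

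- Reading A: keep a variant if it is (somatic and rare) or (homozygous, whatever its origin).
- Reading B: keep a variant only if it is somatic and is either rare or homozygous.

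**Step 2: apply it.**

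| Variant | Reading A | Reading B |
|---|---|---|
| Rare somatic variant in tumor | kept | kept |
| Homozygous germline variant | kept | dropped |
| Heterozygous germline variant in buccal DNA | dropped | dropped |
| Germline variant with the other allele lost in tumor | kept only if zygosity is judged in tumor DNA | dropped on a strict reading, because the variant is germline |
| Germline variant plus a rare somatic second hit in the same gene | somatic hit kept, so the gene is flagged; germline variant dropped | same |

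The third row is the result that matters, and it does not depend on the reading. The fourth and fifth rows show how some carriers could still be flagged through the tumor. The plan does not say in which sample zygosity is judged, so the fourth row cannot be settled from the text.

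**Step 3: what follows the filter.** The Wald test comes in the next sentence. The plan does not say outright that the test uses only the filtered variants; the order of the sentences implies it.

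**Step 4: compare with the objective.** Section 2.3 asks for mutational analysis of germline DNA. The exome paragraph is the only described method for the buccal DNA, and no separate germline method is given anywhere. The stated rule therefore works against the stated aim.

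**Step 5: who is affected.** Subjects with an earlier positive BRCA test are identified under section 3.1 whatever the filter does. The group at risk is carriers without an earlier test and without a second hit or allele loss visible in tumor. The documents give no count of untested subjects and no carrier rate among them. The figure of about 30% in section 1.3 pools mutation carriers with tumors that only resemble BRCA-deficient ones in expression, so it cannot serve as a carrier rate.

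**The case against.** The strongest reply is that the paragraph describes a tumor-variant filter. Calling a variant somatic needs a matched normal, and buccal DNA serves as one. On that view nothing was meant to be tested in the buccal sample itself, and a carrier whose tumor has a second hit, or has lost the other allele, may still be flagged. The paragraph is also a short summary of exploratory work. Filtering comes after sequencing, so nothing is irreversibly lost, and section 7.1 leaves room for a later plan.

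Much of this stands. Some carriers may be recovered through the tumor, and the sequence data could be filtered again. But the matched-normal reading leaves the germline objective with no method at all, and untested carriers whose tumors show no second event can still be counted as unaltered. The later plan is conditional and carries no commitment on germline variants, so the written rule is what stands.

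A reader might also infer that the filter prevents the trial from learning whether benefit is confined to BRCA carriers. The documents do not support that. Earlier BRCA results are collected and can be used without exome data, and the trial is not sized for that question: each arm of 30 is planned for a test of median PFS of 2 against 4 months (section 7.1). Nor is BRCA deficiency the only stated basis for expecting activity. Sections 1 and 1.2 rest the hypothesis on response to platinum, sections 1 and 1.3 also cite BRCA-like expression profiles, and section 1.5.3 reports activity of the combination in patients without germline BRCA mutations. Section 5.12.3 adds an immunohistochemical assay of homologous-recombination deficiency in tumor, though that does not give germline status.

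**Conclusion.** The point holds in a limited form. Under either reading, the filter removes heterozygous germline variants in buccal DNA, BRCA1/2 included, and so defeats an exploratory objective for which no other method is described. Carriers without an earlier BRCA test can be misclassified as unaltered unless the tumor shows a second event.

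Its size cannot be given. It is tempting to use the cap of 10 known carriers among 60 subjects (10/60 = 16.7%), but that figure describes people whose status is already collected; it neither counts nor bounds the untested carriers.

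The conclusion assumes that the Wald test is run on the filtered variants, as the sentence order implies, and that the filter applies to buccal as well as tumor data, as the text reads. If the filter is meant for tumor data only, the misclassification of untested carriers remains possible and the gap becomes a missing germline method. The primary PFS test and the sample size are unaffected. This is a minor point, worth correcting because the correction is cheap.

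**What to change.** Amend the filter in section 5.12.3, or set the rule in the analysis plan for the genetic research that section 7.1 foresees, so that it does three things:

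1. It retains, besides what is kept now, pathogenic or likely pathogenic germline variants, heterozygous included, at least in BRCA1/2. Extending this to other homologous-recombination genes is optional and would need a gene list.
2. It states in which sample, tumor or buccal, zygosity is judged.
3. It combines the germline result with the earlier BRCA test results into one BRCA status for the exploratory response analyses.

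The cost is a written variant-classification rule and slightly more analysis work. The swabs and the sequencing are already planned, so no new sample or assay is needed.

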3.8 Evaluation and calculation of variables

The primary efficacy outcome measure is as follows:

- PFS (progression free survival) defined as the time from randomization to the first occurrence of disease progression (as determined using RECIST 1.1 criteria and assessed by the Investigator) or death from any cause on study. Death on study is defined as death from any cause within 30 days of the last dose of study treatment regimen. Tumor progression will be assessed locally at each site by the investigators according to RECIST 1.1. No independent review of tumor progression is planned. PFS with disease progression determined by iRECIST for patients on the combination arm will also be examined in exploratory data analysis.

The secondary efficacy outcome measures in all subjects are as follows:

- OS (overall survival) defined as the time from entry onto trial until death from any cause.
- ORR (overall response rate) defined as the subjects achieving Complete Response or Partial Response as defined by RECIST 1.1.
- CBR (clinical benefit rate) defined as subjects achieving Complete Response, Partial Response or Stable disease \geq 24 weeks

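### Wald testing of rare gene alterations against a binary response breaks down when every carrier responds, so the exome screen could drop its strongest predictors

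*Combined protocol and SAP*

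**What the plan says.** In the combined protocol and SAP, section 5.12.3 (whole exome sequencing) first describes how variants will be selected. They are classified, and "then will be narrowed by retaining only somatic rare variants and homozygous mutations". The next sentence gives the only inferential method for these data: "Wald testing will initially be used to define relationships between gene alterations and response to therapy". It names no model, effect scale, minimum carrier count or multiplicity control, and it does not say which response variable is meant. The nearest candidate is the ORR component in section 3.8, "defined as the subjects achieving Complete Response or Partial Response as defined by RECIST 1.1".

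On numbers, section 7.1 says that "the sample size per arm will be inflated to 30 subjects, for a total of 60 subjects", and section 3.1 words the target as approximately 60. Section 7.1 adds that "The number of subjects that will agree to participate in the genetic research is unknown". It therefore cannot yet say "whether sufficient data will be collected to allow a formal statistical evaluation or whether only descriptive statistics will be generated", and it promises an analysis plan where appropriate. Section 3.1 also collects earlier BRCA results "previous BRCA test data will be collected to ascertain the number of known BRCA mutation carriers -- which will be limited to 10 in total".

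**The concern.** A Wald test divides an estimate by its standard error and relies on both behaving well. With rare variants in about 60 subjects, many genes will have only a handful of carriers. It can then happen that every carrier responds. In a logistic model the estimated log odds ratio is then infinite, the reported standard error is enormous, and the ratio falls towards zero. The p-value approaches 1 for what may be the clearest association in the data.

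Section 5.12.3 places the Wald test at the initial step. An initial screen usually decides which genes are looked at again, so a gene lost there may not be recovered later.

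**Working it through.** **Inputs.** From the documents: 25 per arm inflated by 20% is 25 × 1.2 = 30 per arm, and 2 × 30 = 60 in total (section 7.1). The genetic analysis has no sample size or power figure of its own to reproduce. Assumed, because the documents are silent: binary response (CR/PR), a logistic model, 3 to 6 carriers per gene, and response rates of 15% to 30%.

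**Formula.** Let a of m carriers and b of k non-carriers respond. The odds ratio estimate is a(k − b) / [(m − a)b], and the squared standard error of its logarithm is 1/a + 1/(m − a) + 1/b + 1/(k − b). If a = m, the term 1/(m − a) has no finite value. Software then reports whatever it has reached when its iterations stop.

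**Step 1: all carriers respond, 5/5 against 6/55.**
- Wald: log odds ratio about 23.7, standard error about 13,000, p about 0.999.
- Fisher: C(11,5)/C(60,5) = 462/5,461,512 = 8.5e-5.
- Likelihood ratio: maximised log-likelihoods are −18.95 (two rates) and −28.58 (one rate), so the statistic is 2 × 9.63 = 19.3 and p = 1.1e-5.
- Firth penalised likelihood ratio: p = 3.2e-5.

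With 3/3 against 6/57 the pattern is the same: Wald 0.999, Fisher 0.0025, likelihood ratio 0.00044, Firth 0.00088.

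**Step 2: the Wald result is not stable.** For 5/5 against 0/55 the p-value depends on where the fit stops: 0.69 after 8 iterations, 0.98 after 15 and 0.9998 after 25. Fisher gives 1.8e-7.

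**Step 3: one carrier fails to respond, 4/5 against 6/55.** Log odds ratio = ln(4 × 49 / (1 × 6)) = 3.486. Standard error = √(1/4 + 1 + 1/6 + 1/49) = 1.199. So z = 2.91 and p = 0.0036, against Fisher 0.0020. Without separation the Wald test works.

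**Step 4: power for a truly strong predictor.** Exact enumeration with N = 60, 5 carriers, 15% response in non-carriers and 5% two-sided, counting separated tables as non-significant for Wald:

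| Carrier response rate | Chance all 5 respond | Wald | Fisher |
|---|---|---|---|
| 80% | 0.80^5 = 33% | 55% | 88% |
| 95% | 0.95^5 = 77% | 22% | 99% |
| 100% | 100% | 0% | above 99.9% |

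In this range, Wald power falls as the association strengthens.

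**Step 5: separation when carriers respond at the overall rate p.** The chance of a separated carrier group is p^m + (1 − p)^m. Over m = 3 to 6 and p = 15% to 30% it runs from 12% to 62%. Its parts are very unequal:
- all carriers respond, p^m: from 0.15^6 = 0.001% to 0.30^3 = 2.7%;
- no carrier responds, (1 − p)^m: from 0.70^6 = 12% to 0.85^3 = 61%.

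In the second kind of table, with N = 30 or 60 and the same ranges, Fisher's p-value runs from 0.14 to 1.0. It would not be significant either.

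**The case against.** **The model is not stated.** This is the strongest reply. Response to therapy could mean PFS in a Cox model or tumour shrinkage in a linear model, where this kind of separation does not arise in the same way. That stands: the p-value near 1 is conditional on a binary response and a logistic fit. The condition is a natural one, since the logistic model is the usual choice for CR/PR. Another scale for binary response does not rescue the test. On the risk-difference scale, 5/5 against 6/55 gives a difference of 1 − 6/55 = 0.891. The unpooled standard error is √[(6/55)(49/55)/55] = 0.042, so z is about 21 and p about 1e-99, which is a failure in the opposite direction.

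**The method is provisional.** Wald testing is only the initial step, and section 7.1 leaves open a purely descriptive analysis and promises a plan where appropriate. This softens the point but does not remove it: a screen that loses the strongest predictors does its harm at the first step, and no genetic analysis plan is among these documents. A standard error in the thousands is also a visible warning, although it is easier to miss across an exome-wide run.

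**A reader might infer that 12% to 62% of true signals are lost.** The documents and the arithmetic do not support that. The figure assumes no association, and almost all of it is tables in which no carrier responds, where an exact test would also be non-significant. It should not be cited as a rate of lost signals.

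**A reader might also infer that a stated objective on resistance or response gets a wrong answer.** In section 2.3 that wording belongs to the item on banking tissue for future research. The exome sequencing objective is to characterise biomarkers.

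**Conclusion.** The point holds in conditional form. If response is CR/PR and the Wald test comes from a logistic model, an alteration whose carriers all respond gets a p-value near 1 where exact and likelihood-based tests give clear evidence (about 0.999 against 8.5e-5 for 5/5 versus 6/55). The loss falls on truly strong predictors: with 5 carriers and a 95% carrier response rate, power is 22% instead of 99%. Alterations for which no carrier responds are hardly affected by the choice of test.

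Carrier counts, response rates and the model are assumptions, and few carriers make separation likely but not certain. The planned total is approximately 60, and the number in the genetic analysis is unknown. Nothing here touches the primary PFS test, the secondary endpoints, safety or the sample size. This is a minor improvement to an exploratory analysis, and it is worth making because it costs almost nothing.

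**What to change.** In section 5.12.3, or in the genetic analysis plan that section 7.1 foresees, state the response variable. For binary response, replace Wald testing with one of two methods, pooled over arms:

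- Fisher's exact test; or
- Firth-penalised logistic regression with arm as a covariate and profile-likelihood p-values.

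Report false-discovery-rate q-values across the genes tested, and set a minimum number of carriers below which a gene is only described. Settle this before the exome data are analysed.

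The cost is a sentence or two of text, with no new data and no change to trial conduct. Fisher's test is slightly conservative and does not itself adjust for arm. The Firth model does adjust, but needs software that supports it.
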